15.4.2 Other Laboratory Parameters

All other parameters collected on the eCRF will be listed in dedicated listings presenting all corresponding collected information on the eCRF.

- Coagulation: activated partial thromboplastin time (aPTT) and prothrombin time (internationalized normalized ratio) (INR).
- Urinalysis: macroscopic appearance, bilirubin, blood, color, glucose, ketones, leukocyte esterase, nitrite, pH, protein, specific gravity, urobilinogen, microscopic evaluation
- Other parameters: hormone (thyroid stimulating hormone (TSH) and free thyroxine (T4)) and totality of binding ADA
- Pregnancy test
- Bone growth assessments (bone density, T-score, Z-score, bone age, insulin-like growth factor (IGF)-1, IGF binding protein-3, 25-hydroxy vitamin D, luteinizing hormone, follicle-stimulating hormone, estradiol, testosterone)

The listings of laboratory results will be provided for all laboratory parameters. The listings will be sorted by parameters and assessment dates or visits for each subject. Laboratory values that are outside the normal range will also be flagged in the data listings, along with corresponding normal ranges. A listing of CTCAE grading will also be generated for those laboratory tests.

In addition, listings of abnormal values will be provided for hematology and chemistry values. If there is at least one abnormal assessment for any parameter, all the data for that laboratory parameter will be included in the listing.

For all tests not mentioned above but present in the clinical data, a listing of subjects with at least one result for the relevant test will be provided.

15.5 Vital Signs (Secondary Endpoint)

A subject data listing will present all vital sign information collected on the eCRF.

15.6 Other Safety or Tolerability Evaluations

15.6.1 ECG

All ECG assessments will be listed.

15.6.2 Quality of Life

Quality of life is assessed at the Screening, Cycle 1, Cycle 2, Cycle 3 visit and every visit until the End of Treatment visit, as well as the safety follow-up visit 30 days after last treatment. The Lansky performance scale will be used to assess subject's quality of life for those ≤ 16 years of age, and the Karnofsky performance scale will be used for subjects > 16 years of age. Both scales assess quality of life using a rating from 0-100, with 0 being a low quality of life and 100 being a high quality of life. Listings including all quality of life data will be provided.

16 Analyses of Other Endpoints

16.1 Pharmacokinetics (Secondary Endpoint)

Analysis Set: PK analysis set

16.1.1 PK Concentration Data

Pre-dose samples that occur before the first drug administration will be assigned a time of 0 hours, as if the sample had been taken simultaneously with the study drug administration.

Values below the lower limit of quantification of the assay (LLOQ) will be taken as zero for summary statistics of PK concentration data. Missing concentrations (e.g. no sample, insufficient sample volume for analysis, no result or result not valid) will be reported and used generally as "N.R."

PK concentrations which are questionable due to a protocol deviation (as defined in the CTP), documented handling error or analytical error (as documented in the bioanalytical report) may be excluded from the PK analysis if agreed upon prior to performing a statistical analyses. In this case the rationale for exclusion must be provided in the Clinical Study Report (CSR). Any other PK concentrations that appear implausible to the Pharmacokineticist/PKPD Data Analyst must not be excluded from the analysis. Any implausible data will be documented in the Clinical Study Report (CSR).

Based on Table 2 (Schedule of Assessments – Pharmacokinetic and Antidrug Antibody Sampling) of the CSP, the timepoint window for the EOI and 3-hour samples is ± 30 minutes. Samples that are collected outside the specified time windows will be included in the PK parameter estimation (NCA) but will be excluded from the concentration summary and mean concentration plots.

Serum avelumab PK concentration data will be listed and summarized by dose level, day and nominal time using standard descriptive statistics including the number of non-missing observations (N), arithmetic mean (Mean), standard deviation (SD), coefficient of variation (CV%), minimum (Min), median (Median), and maximum (Max).

Individual concentration-time profiles showing all subjects by dose level will be created using the actual time points and the numeric concentration data. Arithmetic mean concentration-time profiles by dose level/cohort will be provided using scheduled (nominal) time points and the numeric concentration data. All concentration-time plots for PK data will be presented both on a linear and on a semi-logarithmic scale. Mean plots will include SD error bars when plotted on a linear scale.

16.1.1.1 Presentation of PK Concentration data

PK concentration data will be descriptively summarized by using: N, Mean, SD, CV%, Min, Median, and Max.

Descriptive statistics of PK concentration data will be calculated using values with the same precision as the source data, and rounded for reporting purposes only. The following conventions will be applied when reporting descriptive statistics of PK/PD concentration data:

Mean, Min, Median, Max:	3 significant digits
SD:	4 significant digits
CV%:	1 decimal place

16.1.2 Estimation of Individual PK Parameters

Population: PK Analysis Set

Pharmacokinetic parameters will be calculated by the PK/PD Processing Group of QPD, Merck, Darmstadt, Germany, or by a CRO selected by the Sponsor, using standard non-compartmental methods and the actual administered dose. PK parameters will be calculated using the actual

elapsed time since dosing, given with a precision of 14 significant digits or the SAS format Best12. In cases where the actual sampling time is missing, calculations will be performed using the scheduled time. Otherwise, there will be no further imputation of missing data.

Non-compartmental computation of pharmacokinetic parameters will be performed using the computer program PPD[®] version 6.3, or higher PPD[®].

The statistical software SAS[®] (Statistical Analysis System, SAS-Institute, Cary NC, USA, windows version 9.1 or higher) may be used to produce tables, listings and figures and in the calculation of PK Parameters if appropriate.

PK parameters will be listed and summarized by dose level, cycle, and day (if applicable) using standard descriptive statistics.

All statistical analyses and descriptive summaries of pharmacokinetic data will be performed on the PK Analysis Set. The mean concentration-time profiles and PK parameter plots will be plotted using the PK Analysis Set and the individual participant concentration-time profiles will use the Safety Analysis Set. Any PK concentrations excluded from the PK analysis set will be listed and flagged.

The following avelumab PK parameters will be calculated where appropriate:

Symbol	Definition
AUC_{τ}	The area under the concentration-time curve (AUC) over the dosing interval (τ) from $T_1=0$ h to $T_2=336$ h (i.e. 14 days). Calculated using the mixed log linear trapezoidal rule (linear up, log down). For single dose, AUC_{τ} is calculated as a partial area with the defined time range. In multiple dose profiles AUC_{τ} is calculated at steady state from one pre-dose time point to the dosing interval time. In cases where the actual observation time is not equal to the scheduled observation time AUC_{τ} will be calculated based on the estimated concentration at τ hours, and not the concentration at the actual observation time. This parameter is calculated following dosing in Cycle 1, Day 1 only. Unit = $\mu\text{g}\cdot\text{h}/\text{mL}$.
AUC_{τ}/Dose	The Dose normalized AUC over the interval from $T_1=0$ h to $T_2=336$ h. Normalized using actual dose, using the formula AUC_{τ}/Dose . This parameter is calculated following dosing in Cycle 1, Day 1 only. Unit = $\mu\text{g}\cdot\text{h}/\text{mL}/\text{mg}$.
AUC_{0-t}	The area under the concentration-time curve (AUC) from time zero (= dosing time) to the last sampling time (t_{last}) at which the concentration is at or above the lower limit of quantification. Calculated using the mixed log linear trapezoidal rule (linear up, log down). This parameter is calculated following dosing in Cycle 1, Day 1 only. Unit = $\mu\text{g}\cdot\text{h}/\text{mL}$.

Symbol	Definition
$AUC_{0-t}/Dose$	The Dose normalized AUC from time zero to the last sampling time (t_{last}) at which the concentration is at or above the lower limit of quantification. Normalized using the actual dose, using the formula $AUC_{0-t}/Dose$. This parameter is calculated following dosing in Cycle 1, Day 1 only. Unit = $\mu\text{g}\cdot\text{h}/\text{mL}/\text{mg}$.
$AUC_{0-\infty}$	The AUC from time zero (dosing time) extrapolated to infinity, based on the predicted value for the concentration at t_{last} , as estimated using the linear regression from λ_z determination. $AUC_{0-\infty}=AUC_{0-t}+C_{last\ pred}/\lambda_z$ This parameter is calculated following dosing in Cycle 1, Day 1 only. Unit = $\mu\text{g}\cdot\text{h}/\text{mL}$.
$AUC_{0-\infty}/Dose$	The Dose normalized AUC from time zero extrapolated to infinity. Normalised using actual dose, using the formula $AUC_{0-\infty}/Dose$. This parameter is calculated following dosing in Cycle 1, Day 1 only. Unit = $\mu\text{g}\cdot\text{h}/\text{mL}/\text{mg}$.
$AUC_{extra\%}$	The AUC from time t_{last} extrapolated to infinity given as percentage of $AUC_{0-\infty}$. $AUC_{extra} = (\text{extrapolated area}/AUC_{0-\infty})*100$. This parameter is calculated following dosing in Cycle 1, Day 1 only. Unit = %.
C_{EOI}	Concentration at the end of infusion. Unit = $\mu\text{g}/\text{mL}$.
CL	The total body clearance of drug following intravenous administration. $CL = Dose_{i.v.}/AUC_{0-\infty}$. This parameter is calculated following dosing in Cycle 1, Day 1 only. Unit = L/h.
C_{max}	Maximum observed concentration. This parameter is calculated following dosing in Cycle 1, Day 1 only. Unit = $\mu\text{g}/\text{mL}$.
C_{trough}	The concentration observed immediately before next dosing (corresponding to pre-dose or trough concentration for multiple dosing). Unit = $\mu\text{g}/\text{mL}$.
$t_{1/2}$	Apparent terminal half-life. $t_{1/2} = \ln(2)/\lambda_z$. This parameter is calculated following dosing in Cycle 1, Day 1 only. Unit = h.
V_z	The apparent volume of distribution during the terminal phase following intravenous administration. $V_z = Dose/(AUC_{0-\infty}*\lambda_z)$ following dosing in Cycle 1, Day 1 only. Unit = L.
λ_z	Terminal first order (elimination) rate constant. Determined from the terminal slope of the log-transformed concentration curve using linear regression on terminal data points of the curve. This parameter is calculated following dosing in Cycle 1, Day 1 only. Unit = 1/h.

The following PK parameters will be calculated for diagnostic purposes and listed, but will not be summarized:

- The time interval (h) of the log-linear regression ($\lambda_{z\ low}$, $\lambda_{z\ upp}$) to determine λ_z .
- Number of data points (N_λ) included in the log-linear regression analysis to determine λ_z .
- Goodness of fit statistic (Rsqr,adj) for calculation of λ_z .

The regression analysis should contain data from at least 3 different time points in the terminal phase consistent with the assessment of a straight line on the log-transformed scale. PPD best fit methodology will be used as standard. The last quantifiable concentration should always be included in the regression analysis, while any concentrations <LLOQ which occur after the last quantifiable data point should not be used.

The coefficient of determination (Rsqr,adj) should be ≥ 0.8000 and the observation period over which the regression line is estimated should be at least twofold the resulting $t_{1/2}$ itself. If these criteria are not met, then the rate constants and all derived parameters (e.g. CL, and V_z etc.) will be included in the parameter outputs and descriptive statistics but will be flagged and discussed appropriately. Any flags should be included in the study specific SDTM.

Partial areas AUC_τ should be calculated using the scheduled dosing interval, as defined in the CTP. The actual dosing interval calculated from CRF time data should not be used. The following rules apply when calculating the partial area AUC_τ within the observed time interval from T_1 to T_2 :

- If either T_1 or T_2 falls within the time range in which samples were taken, but does not coincide with an observed data point, then a linear or logarithmic interpolation is performed to estimate the corresponding concentration value. Whether a linear or logarithmic interpolation is used will depend on the method of AUC calculation e.g. linear up log down.
- If the end time of the interval (T_2) occurs after the last measurable concentration and the terminal regression (λ_z) is estimable, then λ_z is used to estimate the concentration at time T_2 . The log trapezoidal rule will be used to calculate the area from the last observation time to the end time of the partial area (T_2). If λ_z cannot be estimated the partial area will not be calculated.

Concentrations <LLOQ, which are before the last quantifiable data point, will be taken as zero for calculating the AUC. Pre-dose samples that occur before the first drug administration will be assigned a time of 0 hours, as if the sample had been taken simultaneously with the study drug administration. The same applies to the very first pre-dose sample of a multiple dose study.

The PPD Core Output will be provided in a separate listing.

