### Justification for Dose

The Phase I, dose-finding part of the study will establish the RP2D of avelumab in pediatric subjects. The starting dose will be the same as the recommended adult dosing regimen, 10 mg/kg every 2 weeks. Treatment will continue until confirmed progression, death, unacceptable toxicity, or any criterion for withdrawal occurs. The adult dose was selected as the starting dose in this study for several reasons, as described below.

In a clinical trial of adult cancer subjects treated with avelumab at doses ranging from 1 mg/kg to 20 mg/kg (Study EMR100070-001), the MTD was not reached. A dose of 10 mg/kg every 2 weeks was chosen as the dose regimen expected to achieve > 95% target occupancy in all subjects (refer to Section 5.2 of the IB).

Simulation was conducted based on the adult PopPK model to find a dose that would have exposure similar to that observed in adult population. First-cycle PK data showed that the

exposures were similar or tended to be lower in subjects with lower body weights following administration of avelumab 10 mg/kg iv every 2 weeks. In the first simulation, the clearance (CL) was assumed to be related to body weight as a power function, with exponents of 0.85 on CL and of 1 on volume of distribution (V) as reported in the literature (Deng 2011). An alternative model using estimated exponent (0.565 for CL and 0.472 for central volume) from the adult Pop PK model had been also explored. It had been noted that allometric exponents estimated from data within species (such as adult subjects) were typically smaller than those observed for between-species scaling, which was likely due to a narrower body weight range in adults for a given species (approximately 2- to 3-fold) (Bai 2012). For this reasons, the first simulation with fixed exponents for CL (0.85) and V (1) was considered to be more relevant for a population like children with a wide range of body weights. This model predicted that 10 mg/kg was needed to achieve similar or relatively lower exposure in children to that in adults, and 15 to 20 mg/kg dose would potentially lead to a higher exposure in children than that in the adults. Therefore, 10 mg/kg was recommended for the starting dose to avoid potential overexposure in some of the body weight groups.

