13.1 Exposure to Study Drug

The dose level for avelumab is calculated as actual dose administered/weight (mg/kg). The last available weight of the subject on or prior to the day of dosing will be used.

The duration of avelumab treatment (in weeks) during the study for a subject is defined as:

$$\text{Treatment duration (weeks)} = (\text{last dose date} - \text{first dose date} + 14) / 7$$

The cumulative dose (mg/kg) of avelumab per subject in a time period is the sum of the actual dose levels that the subject received within that period (i.e., total dose administered (mg) / weight (kg)).

Each cycle for avelumab is defined by a 2-week period. The dose intensity (DI) and the relative dose intensity (RDI) will be calculated for each subject across all cycles. The dose intensity per cycle (mg/kg/cycle) is defined as

$$\text{DI (mg/kg/cycle)} = \text{Cumulative dose (mg/kg)} / [\text{duration of therapy (in weeks)} / 2]$$

The relative dose intensity (RDI) is defined as the actual dose intensity divided by the planned dose as specified in the protocol per cycle, denoted in the formula below as “xx”, and expressed in %. The dose level will be determined via the escalation process.

$$\text{RDI (\%)} = 100 \times [\text{DI (mg/kg/cycle)} / \text{xx (mg/kg)}]$$

The summary of treatment exposure and compliance for avelumab will include the following information:

- Treatment duration (weeks)
- Total number of infusions received
- Cumulative dose (mg/kg)
- Dose intensity (mg/kg/cycle)
- Relative dose intensity (%)

A listing of study treatment administration will be provided and will include subject identifier, age, study day, start date and time of the infusion as well as the kit number.

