16.1.2.2 Planned Avelumab PK Outputs

The following listings and summary statistics of avelumab PK concentration and parameter data will be provided, where data permit:

- Individual values and summary of avelumab serum concentrations ($\mu\text{g/mL}$) by dose level, cycle, day, and scheduled time point
- Individual values and summary of single dose PK parameters for avelumab by dose
- Individual values and summary of avelumab C_{EOI} and C_{trough} by dose level
- Summary of avelumab serum concentrations ($\mu\text{g/mL}$) by dose level, cycle, day, and scheduled time point, stratified by weight (<10 kg or ≥ 10 kg)
- Summary statistics of single dose PK parameters for avelumab, stratified by weight (<10 kg or ≥ 10 kg)
- Summary statistics of C_{EOI} and C_{trough} by dose level, stratified by weight (<10 kg or ≥ 10 kg)
- Individual serum concentration-time course (linear and semi-logarithmic scales) by phase, dose level/cohort, cycle, and day, using actual time points (where available)
- Arithmetic mean serum concentration-time course on both linear ($\pm\text{SD}$) and semi-logarithmic scales using scheduled time points – with all dose levels overlaid on the same plot for the single dose in Cycle 1, stratified by weight (<10 kg or ≥ 10 kg)
- Arithmetic mean trough concentration-time course will be plotted on linear ($\pm\text{SD}$) scale using scheduled time points – with all dose levels overlaid, stratified by weight (<10 kg or ≥ 10 kg)

Dose proportionality (if appropriate) will be presented graphically as follows:

- Boxplots for dose-normalized PK parameters (AUC/Dose , C_{max}/Dose and C_{EOI}/Dose) by dose level, stratified by weight (<10 kg or ≥ 10 kg).

- Scatter Plot of individual AUC, C_{max} , and C_{EOI} versus Dose on a log-log scale. A linear regression may also be overlaid.

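### Dose-normalised AUC is defined per absolute mg although children are dosed per kg, so the planned dose-proportionality displays mix body weight with dose

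*SAP*

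**What the plan says.** SAP 16.1.2 obtains the PK parameters "using standard non-compartmental methods and the actual administered dose". Three AUCs are dose-normalised: over the dosing interval, to the last quantifiable sample, and to infinity. Each is divided by the actual dose (for the first, "Normalized using actual dose, using the formula" AUCτ/Dose), and each has the unit µg·h/mL/mg. In the same table CL, described as "The total body clearance of drug following intravenous administration", is dose over AUC to infinity in L/h.

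SAP 16.1.2.2 then says: "Dose proportionality (if appropriate) will be presented graphically as follows". There are two displays.

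- "Boxplots for dose-normalized PK parameters", covering AUC, Cmax and CEOI, by dose level and split at 10 kg.
- A scatter of individual AUC, Cmax and CEOI "versus Dose on a log-log scale. A linear regression may also be overlaid". It has no weight split and no unit for Dose.

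Cmax/Dose and CEOI/Dose appear in the boxplots but are not defined in the parameter table.

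Dosing is by body weight (Protocol 6.2.1). Protocol 5.1.1.1 allows levels of 3, 10 and up to 20 mg/kg. SAP 13.1 derives the actual mg/kg dose for the exposure summaries, but SAP 16.1.2 does not use it.

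**The concern.** Dose level in this trial means mg/kg, but AUC is normalised by mg. At a fixed mg/kg level the mg dose is proportional to weight, so across children most of the spread in mg is spread in body size. Dividing AUC by mg leaves the whole effect of weight on clearance in the result. Plotting AUC against mg puts weight on the same axis as dose.

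A reader of these displays wants to know whether exposure rises in proportion to dose. On a mg scale, a flat scatter or a gap between boxplots could come from body size alone and be read as non-proportional PK. The optional regression line invites that reading most directly. The 10 kg split helps little, because the upper stratum covers most of childhood.

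**Working it through.** The plan states no figure of its own here, so the check is algebra and simulation under PK that is exactly proportional to dose.

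**Inputs from the documents.** Protocol 5.2 gives weight exponents of 0.85 for CL and 1 for volume (preferred for children), with 0.565 and 0.472 as the alternative. The dose levels are those of Protocol 5.1.1.1.

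**Assumptions.** The documents give no weight distribution, between-subject variability or number of subjects per level. I used weights of 5-70 kg, log-uniform (10-70 kg for the upper stratum), 25% log-normal variability, and 6 subjects at 10 mg/kg with 12 at 20 mg/kg for the small-sample runs.

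**Unit of Dose.** µg/mL equals mg/L, so mg divided by µg·h/mL gives L/h. CL in L/h therefore needs Dose in mg; a mg/kg dose would give L/h/kg.

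**Effect of weight at one mg/kg level.** Let W be weight, d the mg/kg dose and b the CL exponent. Then mg = d·W and AUC to infinity ∝ d·W/W^b. So AUC/mg ∝ W^(-b), and AUC/(mg/kg) ∝ W^(1-b). Cmax and CEOI are taken as mg/W^v, with v the volume exponent. For 10 kg against 70 kg:

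| Quantity | Exponent | Per mg | Per mg/kg |
|---|---|---|---|
| AUC | b = 0.85 | 7^0.85 = 5.2-fold | 7^0.15 = 1.3-fold |
| AUC | b = 0.565 | 7^0.565 = 3.0-fold | 7^0.435 = 2.3-fold |
| Cmax, CEOI | v = 1 | 7.0-fold | none |
| Cmax, CEOI | v = 0.472 | 7^0.472 = 2.5-fold | 7^0.528 = 2.8-fold |

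The AUC rows hold exactly for AUC to infinity and only approximately for the two partial AUCs.

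**Scatter slope.** If weight and dose level are independent, the slope of log AUC on log mg is 1 - b·V_W/(V_W + V_d), where V_W and V_d are the variances of log weight and log dose level.

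- V_W for 5-70 kg log-uniform = (ln 14)²/12 = 0.580.
- V_d for equal numbers at 10 and 20 mg/kg = (ln 2/2)² = 0.120.
- V_W/(V_W + V_d) = 0.580/0.700 = 0.83.
- AUC slope = 1 - 0.85 × 0.83 = 0.30, or 1 - 0.565 × 0.83 = 0.53.
- Cmax slope, with v in place of b: 0.17 (v = 1) or 0.61 (v = 0.472).

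A simulation of 1,000,000 subjects agrees: AUC slope 0.296 and 0.531 on mg, and 1.00 for both exponents on mg/kg. Over ranges of 5-70, 5-80 and 10-70 kg, log-uniform or uniform, the AUC slope on mg runs from 0.28 to 0.42 (b = 0.85) and from 0.52 to 0.61 (b = 0.565). For levels of 3 and 10 mg/kg it is 0.48 and 0.65.

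**Scatter in small samples.** Over 5,000 simulated trials of 6 + 12 subjects, the median slope on mg was 0.29 (95% range 0.07 to 0.47) for b = 0.85 and 0.53 (0.35 to 0.69) for b = 0.565. A 95% interval for the slope lay wholly below 1 in over 99% of trials for either exponent, against about 2.5% on mg/kg. With 6 + 6 subjects it was 99.1% and 94.1%.

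**Boxplots, upper stratum.** Over 10,000 trials of 6 against 12 subjects at 10-70 kg, the ratio of medians between levels is centred on 1.0.

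| CL exponent | Scale | Ratio, 5th-95th percentile | Off by more than 1.5-fold | GeoCV |
|---|---|---|---|---|
| 0.85 | per mg | 0.56-1.80 | 26% | 58% |
| 0.85 | per mg/kg | 0.78-1.28 | about 1% | 26% |
| 0.565 | per mg | 0.66-1.51 | 11% | 42% |
| 0.565 | per mg/kg | 0.72-1.43 | 5% | 36% |

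If the levels differ in weight, the ratio shifts. With a typical 40 kg at 10 mg/kg and 15 kg at 20 mg/kg, the ratio per mg (higher to lower level) is (40/15)^b = 2.30 or 1.74, and per mg/kg it is 0.86 or 0.65.

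**The case against.** Four points carry weight.

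- **Unit.** The per-mg unit is explicit only for AUC/Dose. For the scatter axis, and for Cmax/Dose and CEOI/Dose, mg is inferred. This stands as a limit on certainty, but SAP 16.1.2.2 uses Dose and dose level as different terms and nothing there converts Dose to mg/kg. An unstated unit also needs fixing.
- **No planned inference.** The SAP offers an optional line, with no slope estimate, interval or criterion. This stands: the figure of over 99% illustrates how misleading the line would be and is not an operating characteristic of the plan.
- **Other outputs.** Un-normalised parameters are tabulated by dose and by weight stratum (SAP 16.1.2.2), and population PK has a separate plan (SAP 16.1.3). These give a reader another route to the question, but they do not correct the displays at issue.
- **Limited gain from mg/kg.** The boxplots are not biased when weights balance. With the alternative exponents, mg/kg helps AUC only modestly and makes Cmax and CEOI slightly worse. This stands, and it is why a change of unit alone is not enough.

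Per-mg AUC is a valid quantity in itself, being the reciprocal of clearance. The objection is to using it to show proportionality across mg/kg levels.

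**Conclusion.** The point holds. Followed as written, the plan would make exactly proportional PK look clearly less than proportional on a mg axis, with an AUC slope near 0.3 or 0.5 depending on the clearance exponent. In the upper weight stratum it would add avoidable noise to the boxplots, with real distortion if the dose levels differ in weight. Such a difference is plausible with small sequential cohorts whose age range the Safety Monitoring Committee may narrow (Protocol 5.1.1.1.5).

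The direction follows from the protocol's own exponents. The sizes rest on the assumed weights, variability and cohort split, and the scatter result rests on reading Dose as mg.

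The reach is limited. The displays are secondary, descriptive and conditional, and they matter only if at least two dose levels are tested. The exposure-adequacy comparison in Protocol 5.1.1.1 uses un-normalised Cmax, AUC and Ctrough and is unaffected. The change should be made, but no primary endpoint depends on it.

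**What to change.** In SAP 16.1.2 and 16.1.2.2:

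1. State the unit of Dose for every dose-proportionality output, and define Cmax/Dose and CEOI/Dose in the parameter table.
2. For these displays, normalise AUC by the actual mg/kg dose from SAP 13.1, and plot AUC, Cmax and CEOI against that dose.
3. Add plots of AUC, Cmax/CEOI and Ctrough against body weight, coded by dose level, because mg/kg scaling does not fully remove weight.

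The per-mg values can stay in the listings. The cost is SAP wording and minor reprogramming. Weight and the actual mg/kg dose are already derived, so no new data are needed.
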